# report least square group differences
tmt.means <- emmeans(mod.sec.food, ~ intervention)
pairs(tmt.means)

```

MRI lesion counts will be analysed using a negative binomial regression model adjusted for baseline MRI and centre and time to last observed lesion as offset. If observations are censored, the model would be adapted accordingly.

```

library(MASS)

mod.les <- glm.nb(lesions_fu ~ lesions_baseline + intervention + site +
                   offset(log(time_lastObs)), data = secEndpoints)
summary(mod.les)
tmt.means <- emmeans(mod.les, ~ intervention)
pairs(tmt.means)

```

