2.3 Sample Size

One event (relapse or at least one new T2 lesion) is expected in every second PwMS within 12 month in the CG. The 100 events result in a statistical power of 85% for a two-sided significance level of 5%. The assumed HR of 0.55 represents a reduction of 45% by IG compared with the CG. With a mean observation time of 12 month, the 100 events can be expected to be observed in 262 PwMS. Due to the assumption of 20% drop-outs over 1 year, it was planned to randomise 328 PwMS (164 per group).

The blinded sample size recalculation report dated on 15th September 2021 is based on a blinded data export of August 16th 2021 comprising events of 135 included patients at that time ([name] and [name], 2021). In the first definition of the primary endpoint events, only definite relapses were counted. In the second definition, possible relapses were counted, additionally. The first definition resulted in 46 primary endpoint events, while the second resulted in 51 primary endpoint events. The calculation of event rates according to the first definition and an assumed dropout rate of 20% resulted in 250 PwMS (125 per group) that have to be randomized. The calculation of event rates according to the second definition and an assumed dropout rate of 20% resulted in 216 PwMS (108 per group) that have to be randomized. The blinded sample size recalculation report resumed, that a sample size of at least 240 PwMS should be targeted.

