2.7 Timing of Outcome Assessments

Data is collected over a period of 12 months, with a flexible follow-up of up to 24 months in early recruited PwMS. Several measurement time points for outcome assessment are intended. They are calculated based on the randomization date: t_1 and t_0 take place before randomization; V_1 is scheduled in month 1 (30 days after randomization), V_2 in Month 3 (+90 days), V_3 in Month 6 (+180 days), V_4 in Month 12 (+365 days). For early recruited PwMS, V_5 takes place in Month 18 and V_6 in Month 24. After reaching the primary endpoint, t_x takes place. Deviations from the ideal time point are allowed to the degree of ± 28 days. Table 2 displays the assessment of variables within these time points.

Table 2 Assessments and measurement time points

| Instrument | Measurement time points | | | | | | | | |
|-------------------------------|-------------------------|----------------|----------------|----------------|----------------|----------------|-----------------------------|-----------------------------|----------------|
| | t ₋₁ | t ₀ | V ₁ | V ₂ | V ₃ | V ₄ | V ₅ [*] | V ₆ [*] | t _x |
| Demographic Data | X | | | | | | | | |
| MRI | | X | | X | X | X | X | X | |
| Clinical visit | | X | X | X | X | X | X | X | X |
| Relapse history | | X | X | X | X | X | X | X | X |
| Immunotherapy status | | X | X | X | X | X | X | X | X |
| EDSS | | X | | | | X | | | |
| RIKNO | | | | | X | | | | |
| CPS | | | | | | | X | | X |
| Decision satisfaction | | | | | | | | | X |
| Patient activation | | X | | | | X | | | |
| Emotional coping | | X | | | | X | | | |
| Changes in empowerment | | | | | | X | | | |
| Expectancy | | | X | | | | | | |
| Readiness to change | | X | | X | | X | | | |
| HAQUAMS | | X | | | | X | | | |
| EQ-5D-5L | | X | | | X | X | X | X | |
| HADS | | X | | | | X | | | |
| GLTEQ | | X | | | | X | | | |
| BSA-F | | X | | | | X | | | |
| Questionnaire of healthy diet | | X | | X | | X | | | |
| myfood24 | | X | | | | X | | | |
| Process evaluation | X | X | X | X | X | X | X | X | |
| Health economic parameters | | X | | | X | X | X | X | |

*Only in in early recruited PwMS.

3 Statistical Principles

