5.1 Outcome definitions

A full list of outcomes and their timing is described in Section 2.7.

MRI lesion: The lesions are counted on T2-weighted MRI images. An experienced, blinded rater will evaluate MRI scans. At *baseline*, in the case that the number of lesions cannot be accurately determined, the number of lesions is set on 11 if there are more than 10 and less than 20 lesions (analog for every increment of ten). The during follow-up observed lesions are exactly counted.

Hamburg Quality of Life in MS Scale Version 10.0 (HAQUAMS) is a questionnaire for measuring quality of life in PwMS (Gold *et al.*, 2001). It consists of 44 items with mostly 5-point-likert scale. Twenty-eight of the items are subdivided into the six subscales:

- Fatigue: Items 6, 7, 8, 9
- Cognition: Items 10, 11, 12, 13
- Lower extremity: Items 17, 18, 19, 20
- Upper extremity: Items 21, 22, 23, 24, 25
- Communication: Items 29, 30, 31, 32, 33, 34
- Mood: Items 36, 37, 38, 39, 40.

Mean subscale scores are calculated, the total score is built by calculating the mean of the subscale score means: *HAQUAMS total score = mean(mean(upper extremity), mean(lower extremity), mean(fatigue), mean(cognition), mean(communication), mean(mood))*. A high total score indicates low quality of life. In case of missing data, mean substitutions are allowed for missing items.

EuroQol 5-Dimension 5-Level (EQ-5D-5L) is used to measure quality of life additionally and to calculate quality-adjusted life years (QALYs). It generates a descriptive health profile by a 5-digit code with 3125 possible health states assessing the domains mobility, self-care, usual activities, pain/discomfort, and anxiety/depression with 5-point-likert scaled responses from no problems (1) to extreme problems (5) (Herdman, 2011). This health state is transformed into index values using the German validation set. Additionally, the health on the examination day is rated on a scale ranging from 0 (worst health) to 100 (best health) (EuroQol Research Foundation, 2019).

An abbreviated 10-item version of the **Risk Knowledge in Relapsing Multiple Sclerosis V.2.0 (RIKNO)** is used to assess the risk knowledge ([name], 2017). Each item of the RIKNO is scored on a scale from 0 to 2. The total RIKNO score is calculated by summing the scores of all 10 items, ranging from 0 to 20, with higher scores indicating greater knowledge.

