5.3 Missing data

In case of missing data, all PwMS will be analysed following the intention-to-treat principle.

Early study discontinuations will be treated as independent right censoring in the primary analysis. In case of substantial or differential study discontinuations, the validity of the independent censoring assumption will be explored in shared random effects models of the primary endpoint and time to study discontinuation. To handle missing data in baseline variables resp. follow-up assessments, multiple imputation will be applied. Predictive mean matching is used for imputing numeric, logistic regression for binary and polytomous logistic regression for nominal variables. The number of imputations will be set on five and the number of iterations for each imputation will be set on its default value of five.

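### The MRI lesion-count model takes time to the last lesion as its offset, which lesion-free patients do not have, and the code uses a different, undefined time

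*SAP*

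**What the plan says.** SAP section 5.2 (Analysis methods) plans a negative binomial regression of follow-up MRI lesion counts, "adjusted for baseline MRI and centre and time to last observed lesion as offset". The R call that follows has "offset(log(time_lastObs)), data = secEndpoints". The name time_lastObs appears only there. The text then adds "If observations are censored, the model would be adapted accordingly".

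Three other places bear on the offset:

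- Section 5.1 fixes how lesions are counted ("The during follow-up observed lesions are exactly counted") but not over what time.
- Section 2.7 makes follow-up unequal: "Data is collected over a period of 12 months, with a flexible follow-up of up to 24 months in early recruited PwMS".
- Section 5.3 requires that, where data are missing, "all PwMS will be analysed following the intention-to-treat principle".

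**The concern.** The log offset in a count model must carry each patient's time at risk. Because follow-up differs between patients, it cannot be left implicit. The time of the latest new lesion is not time at risk. It ends when an outcome event is seen, so it depends on the response, and for a patient with no new lesion it does not exist. The code name reads more naturally as time to last observation, which would be a proper exposure, but the SAP does not say so.

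Two programmers could therefore produce different analyses, one from the sentence and one from the code. The sentence also leaves open what a lesion-free patient receives: zero, a missing value, or full follow-up. Setting the value to missing would remove most of the sample, and more of the intervention group than of the control group if the programme works.

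**Working it through.** **Design figures (SAP section 2.3).** These serve only to size the lesion-free share; the SAP gives no figure for the lesion model itself.

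- Power with 100 events at HR 0.55, two-sided 5%, 1:1: √100/2 × |ln 0.55| − 1.96 = 2.989 − 1.960 = 1.029, i.e. 84.8% (stated 85%).
- Events for 85% power: 4 × (1.960 + 1.036)² / (ln 0.55)² = 100.5, so 101.
- Mean event probability (0.50 + 0.55 × 0.50)/2 = 0.3875; 101/0.3875 = 260.6, rounded up to equal arms of 131 = 262 (stated 262).
- 262/0.80 = 327.5, so 328 (stated 328).

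The design inputs are reproduced.

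**Patients without a time to last lesion.** An event (relapse or new T2 lesion) "is expected in every second PwMS within 12 month in the CG".

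- Control group event-free at 12 months: 0.50.
- Intervention group under proportional hazards: 0.5^0.55 = 0.683.
- With the target of 240: 120 × 0.50 + 120 × 0.683 = 142 (59%).

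At 12 months this is a lower bound for lesion-free patients, because the composite event also counts relapses. The blinded review in section 2.3 points the same way: 135 − 46 = 89 (66%) or 135 − 51 = 84 (62%) of 135 patients had no event at the export. Longer follow-up in early recruits lowers the share; in the simulations below it was about half to three fifths of patients.

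**Three readings of the offset.** Gamma-Poisson counts were simulated with MRI at months 3, 6 and 12 (plus month 18 or 24 in 0% or 40% of patients) and 20% drop-out per year. The 40% and the following inputs are assumptions, because the SAP gives none of them:

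- Dispersion a = 0.5, 1.5 or 3.
- Control rate (0.5^(−a) − 1)/a, which makes 50% of controls lesion-free at 12 months: 0.83, 1.22 and 2.33 lesions per year.
- Rate ratio 0.55, borrowed from the composite HR, with 0.70 and 1 as alternatives.

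Centre and baseline lesion count were left out.

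| Offset | True 0.55 | True 0.70 | True 1 | Power at 0.55, 240 randomised |
|---|---|---|---|---|
| Time to last MRI | 0.54–0.56 | 0.70–0.72 | 0.98–1.02 | 66–88% |
| Time to last lesion, lesion-free patients dropped | 0.70–0.85 | 0.79–0.91 | 0.98–1.02 | 15–55% |
| Time to last lesion, full follow-up if lesion-free | 0.53–0.58 | 0.70–0.73 | 0.98–1.02 | 58–85% |

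Dropping leaves about 100 of the 227 patients who have a follow-up MRI. The false-positive rate at ratio 1 was 5–6%, 2.5–10% and 3.5–5% in the same order.

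A second simulation compared crude lesions per person-time, with control rates of 0.5 to 2.0 per year and dispersion 1 to 2. For a true ratio of 0.55 it gave 0.53–0.56, 0.69–0.85 and 0.52–0.56.

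**The SAP's model form in R** (one simulated trial, n = 240, 134 lesion-free). With time 0 for lesion-free patients, glm.nb stopped with an error, since log(0) is not finite. With missing times it used 106 patients and gave 0.69, against 0.49 from all 240 with time to last MRI.

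**The case against.** The strongest reply is that this is one wrong word. The model is written out directly below the sentence, its offset reads as time to last observation, and that would be sound. Other variables in the illustrative code are not defined either. The damaging case also requires a statistician to discard every zero from a count model, which few would do. Time 0 would be noticed because the fit fails, and full follow-up for lesion-free patients does little harm. Finally, the SAP has a sentence on censoring and, in section 5.3, multiple imputation.

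Much of this stands as a limit on weight. A slip is the likeliest explanation, the estimates of 0.70 to 0.85 describe one reading only, and the missing definition matters here mainly because text and code disagree.

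It does not remove the defect. The censoring sentence names neither the exposure nor a value for lesion-free patients. Multiple imputation cannot help either: their time to last lesion is not an unrecorded value but one that does not exist, and imputing it from lesion-positive patients would invent an exposure.

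**Conclusion.** The concern holds. Taken literally, the sentence in section 5.2 specifies an invalid exposure, and the code does not resolve it. It should be fixed, but it is not critical.

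- **Firm, from the SAP alone:** text and code name different times, and about 142 of 240 patients would have no value for the worded time at 12 months under the design assumptions.
- **Robust in direction only:** losing lesion-free patients pulls the ratio towards 1. The sizes (0.70 to 0.85 for a true 0.55, and power of 15–55% instead of 66–88%) depend on the assumed rate, dispersion and ratio.
- **Limits:** with full follow-up for lesion-free patients there is little bias and some loss of power. No reading creates a spurious benefit in the estimate. The lesion count is not listed in Table 1, and the primary Cox analysis and listed secondary endpoints are untouched.

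The lesion count will still be read next to the primary result, because new T2 lesions are part of that endpoint. The choice should therefore be settled in writing before the analysis.

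**What to change.** In section 5.2, replace the offset wording with: *log of the time from baseline MRI to the last evaluable follow-up MRI as offset*. Define time_lastObs in exactly that way, with or without new lesions, so that text and code agree. Add that patients with no follow-up MRI, who have neither a lesion count nor this time, are handled under section 5.3; in the simulation these were about 240 − 227 = 13 patients.

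The cost is one sentence and one variable definition. Table 2 already schedules MRI at baseline and months 3, 6 and 12, and at months 18 and 24 for early recruits, so no new assessment is needed and scan dates should be at hand. The primary and Table 1 analyses do not change.

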5.3 Missing data

In case of missing data, all PwMS will be analysed following the intention-to-treat principle.

Early study discontinuations will be treated as independent right censoring in the primary analysis. In case of substantial or differential study discontinuations, the validity of the independent censoring assumption will be explored in shared random effects models of the primary endpoint and time to study discontinuation. To handle missing data in baseline variables resp. follow-up assessments, multiple imputation will be applied. Predictive mean matching is used for imputing numeric, logistic regression for binary and polytomous logistic regression for nominal variables. The number of imputations will be set on five and the number of iterations for each imputation will be set on its default value of five.

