1.4 Secondary objective and endpoint

Key secondary endpoint is quality of life measured by the HAQUAMS. Secondary endpoints are given in Table 1. For further details on the definition of the endpoints, see Section 5.1.

2 Study methods

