5.6 Statistical software

All analyses will be performed in the current version of R or alternatively in SAS (version 9.4 or higher). All R packages are used in their current version and will be reported within the statistical report. For data visualization, *ggplot2* is used. For multiple imputation, *mice* is used.

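### Five imputations with no stated seed are too few for the key secondary endpoint: a result near p = 0.05 can change with the seed, and about 1 to 5 points of power are lost (about 3 in the central case).

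*SAP*

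**What the plan says.** Section 5.3 applies imputation broadly: "To handle missing data in baseline variables resp. follow-up assessments, multiple imputation will be applied". It then fixes the settings: "The number of imputations will be set on five". The iteration count is kept at the software setting: "the number of iterations for each imputation will be set on its default value of five". The method for continuous scores is also given: "Predictive mean matching is used for imputing numeric". Section 5.6 names the package: "For multiple imputation, *mice* is used". No seed appears in 5.3, in 5.6 or in any of the R code in 5.2.

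Three other places determine how much imputation there will be:

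- Section 1.4: "Key secondary endpoint is quality of life measured by the HAQUAMS".
- Table 2 in section 2.7 schedules HAQUAMS at t0 and V4 (month 12) only. Section 5.2 tests it by ANCOVA with baseline and centre.
- Section 2.3 inflates the sample size with the words "Due to the assumption of 20% drop-outs over 1 year" and reports that, after the blinded review, "a sample size of at least 240 PwMS should be targeted".

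**The concern.** A patient lost before month 12 has no other follow-up HAQUAMS value, so under section 5.3 the outcome itself is imputed. With only five imputations, the pooled estimate and its standard error both carry appreciable simulation noise that depends on the random seed. Two analysts who follow the SAP exactly could reach opposite conclusions at the 5% level from the same locked database. With no seed prespecified, that choice also stays open until after the data are seen. The extra noise costs some power as well. What is at stake is the precision and reproducibility of the secondary endpoints analysed on imputed data. The primary Cox analysis is not at stake, because section 5.3 treats early discontinuation as right censoring.

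**Working it through.** **The SAP's own figures.** These concern the primary endpoint; no power is stated for HAQUAMS. With 100 events and HR 0.55, √100/2 × |ln 0.55| = 2.989, and Φ(2.989 − 1.960) = 84.8%, against 85% stated. For dropout, 262/0.8 = 327.5, hence 328. The 20% is therefore used as the SAP describes.

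**Inputs from the SAP.** m = 5; 20% dropout; N = 240; two-sided 5%; ANCOVA with baseline and centre.

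**Inputs assumed.** FMI of 0.10, 0.20 or 0.30; 80% HAQUAMS power with unlimited imputations; complete-data degrees of freedom of 228 (240 patients less an allowance of 12 for model terms).

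**Step 1, noise in the estimate.** Scale the total variance with unlimited imputations to 1. The within-imputation variance is then U = 1 − FMI and the between-imputation variance is B = FMI. Over seeds, the pooled estimate varies with standard deviation √(FMI/m), in units of its standard error (SE). The variation of the SE itself is simulated.

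| FMI | Estimate, m = 5 | Estimate, m = 50 | CV of the SE, m = 5 |
|---|---|---|---|
| 0.10 | √(0.10/5) = 0.141 | 0.045 | 4.1% |
| 0.20 | √(0.20/5) = 0.200 | 0.063 | 7.8% |
| 0.30 | √(0.30/5) = 0.245 | 0.077 | 11.5% |

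**Step 2, a check by hand at FMI 0.20 and m = 5.** Rubin's total variance is T = U + (1 + 1/m)B = 0.80 + 1.2 × 0.20 = 1.04. The missing share is λ = 0.24/1.04 = 0.231. The Barnard-Rubin degrees of freedom combine 4/λ² = 75.1 with (229/231) × 228 × (1 − λ) = 173.9, which gives 52.5 and a critical t of 2.006. Significance therefore needs an estimate of at least 2.006 × √1.04 = 2.046. A stable p of 0.03 (p with very many imputations) corresponds to an estimate of 2.187. The chance of falling short is Φ((2.046 − 2.187)/0.200), or about 24%. Letting the SE vary as well raises this to the simulated 28%.

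**Step 3, simulation of the same model.** 400,000 draws per cell for a fixed stable p; 1,000,000 trials per cell for power and for agreement between two seeds.

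| Quantity | m | FMI 0.10 | FMI 0.20 | FMI 0.30 |
|---|---|---|---|---|
| Seeds giving p ≥ 0.05 when stable p = 0.03 | 5 | 14% | 28% | 37% |
| | 50 | 0% | 0.4% | 2% |
| Seeds giving p ≥ 0.05 when stable p = 0.01 | 5 | 0.1% | 4% | 11% |
| | 50 | 0% | 0% | 0% |
| Two seeds disagree on significance, all trials | 5 | 5.5% | 9.5% | 13.8% |
| | 50 | 1.6% | 2.4% | 3.2% |
| Power | 5 | 78.9% | 77.1% | 74.7% |
| | 50 | 79.9% | 79.9% | 79.7% |

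Type I error at m = 5 is 4.85%, 4.86% and 4.94%.

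**Step 4, the SAP's own imputation method.** Predictive mean matching was simulated with 5 donors, N = 240, 20% of month-12 values missing, a baseline-outcome correlation of 0.6 and 6 centres (both assumed), and no auxiliary variables. Over 20 data sets with a stable p of 0.027 to 0.033, the estimated FMI was 0.185 to 0.221. With m = 5, 28% of seeds gave p ≥ 0.05 (23% to 32% across data sets); with m = 50, 0.5% did. The mean 95% range of p over seeds was 0.009 to 0.112 with five imputations and 0.021 to 0.044 with 50.

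A separate simulation of 3,000 ANCOVA trials with predictive mean matching lost 2.4 points of power with m = 5 against m = 50, and 3.0 points against an ANCOVA of complete cases (standard error about 0.5).

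**The case against.** The strongest reply is that nothing here is invalid. Rubin's rules allow for a small m through the B/m term and the reduced degrees of freedom, so type I error holds and the reported intervals already contain the noise. That is right, and it limits the point to efficiency and reproducibility of secondary analyses.

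Second, the size rests on inputs the SAP does not give. FMI need not equal the dropout rate: Table 2 offers possible auxiliary variables, such as EQ-5D-5L at V3, and 20% is a planning assumption, not observed missingness. At FMI 0.10 the power loss is only about 1 point. If power is 90% and FMI is 0.20, it is 2.2 points. This stands as a reason to quote a range. Even at FMI 0.10, however, about one seed in seven turns a stable p of 0.03 non-significant.

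Third, the large seed effects apply only to results near 0.05. This is also true; across all trials at FMI 0.20, disagreement between two seeds is 9.5%, not 28%.

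Fourth, a missing seed is a programming detail. On its own it would be minor. A seed makes one run repeatable, but it neither removes the dependence on the seed chosen nor recovers power.

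Finally, 20 imputations would recover most of the power: 79.1%, against 79.5% with 50, in a separate calculation at FMI 0.20. But at a stable p of 0.03, two seeds then still disagree in 10% of pairs, against 0.7% with 50.

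**Conclusion.** The concern holds. Five imputations leave the test of the key secondary endpoint dependent on the seed when the result is near 0.05, and they give up about 3 points of power in the central case. The range is about 1 to 5 points for an FMI of 0.10 to 0.30, given 80% power with unlimited imputations. This loss comes on top of the information lost to dropout itself. Validity and the primary analysis are not in question. The change should be made, ahead of unblinding, because it removes an avoidable weakness at almost no cost.

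**What to change.** In section 5.3, replace five imputations with one fixed number of at least 50 (for example, exactly 50), so that the number cannot be chosen after results are seen. Add one sentence that prespecifies the random seed and says it will be reported. The larger number reduces the noise; the seed makes the run repeatable. The number of iterations can stay as written. The cost is one changed number, one added sentence and minutes of computing time, with no effect on data collection or sample size.
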